5.0 Number of Subjects

5.1 The proposed single-site study will be conducted at the University of Houston College of Optometry. Up to 30 subjects will be screened for study inclusion, with the goal of completing 24 subjects.

Source data will be collected on paper case report forms and then double entered electronically into a database by trained personnel prior to locking the dataset for analysis.

5.2 In this within-subject crossover design, a paired T-test will be used to compare visual acuity performance, contact lens discomfort, subjective visual quality and LTB4 concentration following toric lens wear to spherical contact lens wear. We will use a two-sided independent T-test to ensure there are no carry over or period effects in our cross-over design, although it is not anticipated. As a secondary outcome, subjects will be asked their preference of contact lenses in a two-alternative forced choice format.

FULL PROTOCOL TITLE: Toric Contact Lens Digital Performance and Comfort Study

One-sample binomial tests will be used to test the hypothesis that the probability of preference to toric lens and spherical lenses are equally likely. Linear mixed model or generalized linear model, as appropriate, will be carried out to examine the associations between eye comfort, visual performance, subjective visual quality and LTB4 concentration during toric and spherical contact lens wear.

We aim to test the hypothesis that $H_0: \Delta=0$ v. $H_1: \Delta \neq 0$ using a two-sided test with significance level $\alpha=0.05$, where Δ is the underlying benefit for treatment contact lenses versus spherical contact lenses in this cross-over design. Our previous work found that toric correction improved visual acuity compared to spherical correction by 6 and 11 letters for high and low contrast logMAR, respectively ($P < 0.001$).¹⁰ To demonstrate an improvement of this amount or more it will require at least 24 and 15 subjects with a $P=0.05$ and 80% power. The dynamic visual acuity test is novel and has not been used previously to allow sample size estimates. A total of 30 subjects will be enrolled to allow for up to 20% dropout/screen-failure/missing data and have 24 subjects complete. We will randomize an equal number of subjects to each group (i.e., group A receives treatment 1 in period 1 and treatment 2 in period 2; group B receives treatment 2 in period 1 and treatment 1 in period 2).

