8.0 Study Timelines

8.1 The total duration of an individual subject's participation in the study will be less than 1 month. The study will consist of 5 visits. Visit 1 will be a baseline evaluation, pre-fitting assessment, randomization, and contact lens fitting. Visits 2 and 4 will be contact lens follow-ups. Visits 3 and 5 are outcome visits and will be performed after 6-8 hours of contact lens wear to provide consistent duration of lens wear between subjects and lens types. The 6-8 hours of wearing time also allows a better understanding of end of day visual performance and the changes in LTB4. Expected visit timing is summarized in the table below:

| |
|---------------------------------------|
| Anticipated Visit Timing and Duration |
|---------------------------------------|

FULL PROTOCOL TITLE: Toric Contact Lens Digital Performance and Comfort Study

| Study Window | Study Visit | Duration |
|--------------|---|---------------|
| Day 1 | Visit 1: Baseline, randomization, contact lens fitting, tear collection | 140 minutes |
| Day 3 ± 1 | Visit 2: Contact lens follow-up | 30-50 minutes |
| Day 10 ± 2 | Visit 3: Outcome lens #1, subjective and objective visual assessments and tear collection, re-fit to lens #2 | 95 minutes |
| Day 13 ± 2 | Visit 4: Contact lens follow-up | 30-50 minutes |
| Day 20 ± 2 | Visit 5: Outcome lens #2, subjective and objective visual assessments and tear collection and tear collection | 75 minutes |

The anticipated duration to enroll and complete all study subjects is approximately 9-12 months. The estimated date for the investigators to complete analyses for this study is Fall/Winter 2021.

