9.0 Study Endpoints

9.1 The primary study endpoints will compare toric to spherical lenses for:

- Near visual acuity

The secondary study endpoints will compare toric to spherical lenses for:

- Other near visual performance outcomes
 - Reading speed, reading sentences acuity, digital device interaction, dynamic visual acuity
- Subjective eye comfort and visual acceptance during contact lens wear
 - Association between subjective comfort surveys and tear TLB4 concentration

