9.2 This is a minimal risk study so safety endpoints are not required

10.0 Procedures Involved

10.1 The study is a clinical trial and will be registered on ClinicalTrials.gov prior to subject enrollment.

10.2 Patients will be seen for 5 visits over a period of approximately 1 month. Visit 1 will determine subject eligibility for the study. Visits 2 and 4 are contact lens follow-up visits. Visits 3 and 5 are study outcome visits. Tests of visual performance at a near reading distance will be evaluated with an iPad application developed by [name]. These applications are designed for research purposes only and are not commercially available. The applications can measure reading speed and provide information on how a subject interacts with the electronic device (e.g. blink rate, working distance from the device, scrolling and zooming on the page, etc.).

10.3 Subjects will be randomized to start with either toric lenses or spherical correction (FDA approved lenses will be utilized).

Overview of Visit Procedures (Assessments)

FULL PROTOCOL TITLE: Toric Contact Lens Digital Performance and Comfort Study

A masked examiner will perform all outcome measures.

| | Visit 1 Baseline and Fit Lens 1 | Visit 2 day 3±1 | Visit 3 – day 10±2 | | Visit 4 day 13±1 | Visit 5 day 20±2 |
|--|--|-------------------------|-----------------------|---------------|-------------------------|---------------------|
| | | Follow- up Lens 1 | Outcomes Lens 1 | Fit Lens 2 | Follow- up Lens 2 | Outcomes Lens 2 |
| Informed consent | X | | | | | |
| Ocular/medical/contact lens history | X | | | | | |
| Ocular symptoms (CLDEQ-8) ⁸ | X | | X | | | X |
| Auto-refraction and keratometry | X | | | | | |
| Slit lamp exam with NaFl staining | X | | | | | |
| Manifest refraction | X | | | | | |
| Accommodation and phoria | X | | | | | |
| Near logMAR HCHL & LCHL acuity OU | X | | X | | | X |
| NAVQ survey ⁵ | X | | X | | | X |
| Radner reading sentences, dynamic acuity measurement and functional vision test with iPad ⁴ | X | | X | | | X |
| Tear collection | X | | X | | | X |
| Study lens order randomization | X | | | | | |
| Insertion of CL and settling (15 min) | X | | | X | | |
| Clinical CL vision and fit assessment, over-refraction, and power adjustment if indicated | X | X | | X | X | |
| Removal of study lens and slit lamp exam with NaFl staining | | X | X | | X | X |

FULL PROTOCOL TITLE: Toric Contact Lens Digital Performance and Comfort Study

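### Protocol 5.2 permits a generalized linear model with no subject effect for the comfort, vision and LTB4 associations, although each subject contributes two correlated records

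*Protocol*

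**What the plan says.** Protocol 5.2 describes a crossover in which every subject wears both lens types: "In this within-subject crossover design, a paired T-test will be used to compare visual acuity performance". For the association objective it gives two candidate models, "Linear mixed model or generalized linear model, as appropriate, will be carried out to examine the associations", to be applied "between eye comfort, visual performance, subjective visual quality and LTB4 concentration during toric and spherical contact lens wear". It gives no rule for choosing between them and names no subject term, clustered standard error or GEE for either. It also does not say whether the two visits are pooled or analysed lens by lens.

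Protocol 8.1 places the measurements: "Visits 3 and 5 are outcome visits and will be performed after 6-8 hours of contact lens wear". The procedures table in Section 10 schedules CLDEQ-8, NAVQ, near acuity, the iPad tests and tear collection at both of these visits. Section 9.1 lists under the secondary endpoints: "Association between subjective comfort surveys and tear TLB4 concentration" (the marker is written LTB4 elsewhere).

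The SAP specifies a linear mixed model only for differences between lens designs, with sequence and lens as fixed factors. It does not mention the association analysis.

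**The concern.** Whether the outcome is non-normal and whether the records are repeated within subject are separate questions. The wording in 5.2 makes the remedies alternatives: a mixed model handles the repetition, while a GLM handles the distribution. The variables here are questionnaire scores, acuity measures and an assay concentration, so moving from a linear model to a GLM because of their distribution is an obvious step. Taken literally, that step drops the subject effect and counts 24 subjects as 48 independent records.

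The stake is the LTB4, comfort and vision associations, a stated aim of the study with one association listed under the secondary endpoints. With standard errors that are too small, chance associations would be reported as significant more often than 5% of the time, and 95% intervals would cover less than 95%.

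**Working it through.** The plan gives no sample size, power or error rate for the association analysis, so there is no figure of its own to reproduce.

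**Inputs**
- Subjects: 24 completers (Protocol 5.2: "A total of 30 subjects will be enrolled to allow for up to 20% dropout/screen-failure/missing data and have 24 subjects complete"; 30 × 0.80 = 24).
- Records per subject: 2 (Protocol 10.2: "Visits 3 and 5 are study outcome visits"). Pooled: 24 × 2 = 48.
- Test level: 0.05, two-sided. Protocol 5.2 states this for the lens effect ("using a two-sided test with significance level"); the SAP also uses 0.05.
- ICCs of predictor and outcome, ρx and ρy: not in the documents. They are assumed and varied over 0 to 1.

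**Step 1, variance.** With two records per subject and no true association, the true slope variance exceeds the variance reported by an unclustered fit by the factor V = 1 + ρx·ρy.

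**Step 2, standard error.** Reported SE ÷ true SE = 1/√V. The same ratio applies to interval width.

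**Step 3, error rate.** Type I error = 2·[1 − Φ(1.96/√V)]. For ρx = ρy = 0.5: V = 1.25, √V = 1.118, 1.96/1.118 = 1.753, error = 8.0%.

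**Step 4, simulation.** 24 subjects × 2 visits, no true association, lens-adjusted Gaussian fit, 60,000 runs per row.

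| ρx, ρy | V | Reported/true SE | Error, formula | Error, simulated |
|---|---|---|---|---|
| 0, 0.8 | 1.00 | 1.00 | 5.0% | 5.0% |
| 0.3, 0.3 | 1.09 | 0.96 | 6.1% | 6.0% |
| 0.3, 0.7 | 1.21 | 0.91 | 7.5% | 7.3% |
| 0.5, 0.5 | 1.25 | 0.89 | 8.0% | 7.9% |
| 0.7, 0.7 | 1.49 | 0.82 | 10.8% | 11.0% |
| 0.9, 0.9 | 1.81 | 0.74 | 14.5% | 14.7% |
| 1, 1 (limit) | 2.00 | 0.71 | 16.6% | 17.4% |

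Both ICCs must be well above zero for the error to matter; one high ICC alone does nothing.

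**Step 5, one model per lens.** With one row per subject in each fit, the same simulations gave 4.8-5.1%.

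**Step 6, the lens term.** Lens varies only within subject, so ignoring the pairing works the other way: V = 1 − ρy. At ρy = 0.5, 1.96/√0.5 = 2.77 and the error is 0.6%, which is conservative. The inflation concerns slopes between measured variables.

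**Step 7, after the change.** In 600 runs at each of ρx = ρy = 0.5, 0.7 and 0.9 (Monte Carlo error about ±2 points):

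| Model | 0.5 | 0.7 | 0.9 |
|---|---|---|---|
| Pooled, no subject effect | 8.3% | 12.2% | 14.7% |
| Linear mixed model, random subject intercept | 6.3% | 5.8% | 5.3% |
| GEE, uncorrected robust SE | 12.2% | 12.2% | 10.3% |

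Uncorrected GEE is therefore not a remedy at 24 subjects. The generalized linear mixed model was not itself simulated; the check of the remedy is on the Gaussian mixed model.

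**The case against.** The strongest reply is that the plan permits a weak analysis but does not prescribe one. It names the mixed model first and leaves the choice to judgement. The paired t-test for discomfort, visual quality and LTB4 shows that the authors know the data are paired, and the only model the SAP specifies for the lens comparison is a linear mixed model. A GLM fitted per lens would be valid, and one with clustered standard errors is not excluded. The aim is worded as exploration, and no sample size depends on it.

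Most of this stands, and it rules out three stronger readings.

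- A reader might infer that the plan treats the two visits as independent. No sentence says so; it leaves that open.
- A reader might infer that the GLM is the branch most likely to be used. The documents give no basis for ranking the two.
- A reader might infer a false-positive rate of 8-16% outright. That range needs ICCs of roughly 0.5 to 0.97 in both variables, and the documents report none. Eligibility is also narrow (baseline CLDEQ-8 below 12, acuity 20/25 or better, cylinder -0.75 to -1.50), which tends to reduce between-subject spread and hence the ICCs for comfort and acuity. A gamma log-link fit gave 9.9%, 12.7% and 16.5% at ICCs of 0.5, 0.7 and 0.9. However, with no within-subject correlation (log-scale SD 0.5, assumed) such a fit already rejected 6.8%, so part of that excess is small-sample Wald behaviour. The Gaussian figures are the ones to rely on.

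What does not stand is that leaving the choice to judgement closes the gap. Offering a mixed model as the first option makes sense only if both visits are pooled, and on pooled visits the named alternative has no subject effect. The SAP does not repair this.

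**Conclusion.** The point holds as a conditional one. Protocol 5.2 permits a model that is invalid for paired records if it is fitted to the pooled visits without a subject effect, and neither document says how within-subject correlation would then be handled. Under that fit, with positive ICCs in both variables and 24 completers, type I error for an association slope lies between 5% and about 17%: about 6% with both ICCs at 0.3, and 8-15% with both between 0.5 and 0.9. At ICCs of 0.5 to 0.9, intervals would be 0.89 to 0.74 of their proper width. All the ICCs are assumptions.

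The effect is confined to a secondary, exploratory analysis. The primary toric-versus-sphere comparison of near acuity does not use this model. The change is still worth making, because a better-suited model is available at almost no cost.

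**What to change.** In Protocol 5.2:
- Replace the generalized linear model option with a generalized linear mixed model with a random intercept for subject, or GEE clustered on subject with a small-sample correction.
- State that the linear mixed model also has a random intercept for subject.
- Keep lens as a fixed factor.
- Carry the same sentence into the SAP, which at present has no association analysis.

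The cost is one sentence in each document and somewhat wider confidence intervals for the associations. No new data are needed. If the associations have already been analysed with an unclustered GLM on pooled visits, they can be refitted from the existing dataset.

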6.0 Recruitment Methods

6.1 Potential subjects will be recruited from the patients and staff of the University Eye Institute/University of Houston College of Optometry, as well as the surrounding community via verbal communication, print media (e.g. study fliers,), telephone and electronic media (e.g. email or posting of study flyer).

6.2 Potential subjects will be screened via phone call.

6.3 Verbal communication, print media (e.g. study flyer), telephone and electronic media (e.g. flyer sent by email, or posted to social media) will be used. (Flyer and phone script are included in this application)

7.0 Multi-Site Research Communication

N/A

8.0 Study Timelines

8.1 The total duration of an individual subject's participation in the study will be less than 1 month. The study will consist of 5 visits. Visit 1 will be a baseline evaluation, pre-fitting assessment, randomization, and contact lens fitting. Visits 2 and 4 will be contact lens follow-ups. Visits 3 and 5 are outcome visits and will be performed after 6-8 hours of contact lens wear to provide consistent duration of lens wear between subjects and lens types. The 6-8 hours of wearing time also allows a better understanding of end of day visual performance and the changes in LTB4. Expected visit timing is summarized in the table below:

| |
|---------------------------------------|
| Anticipated Visit Timing and Duration |
|---------------------------------------|

FULL PROTOCOL TITLE: Toric Contact Lens Digital Performance and Comfort Study

| Study Window | Study Visit | Duration |
|--------------|---|---------------|
| Day 1 | Visit 1: Baseline, randomization, contact lens fitting, tear collection | 140 minutes |
| Day 3 ± 1 | Visit 2: Contact lens follow-up | 30-50 minutes |
| Day 10 ± 2 | Visit 3: Outcome lens #1, subjective and objective visual assessments and tear collection, re-fit to lens #2 | 95 minutes |
| Day 13 ± 2 | Visit 4: Contact lens follow-up | 30-50 minutes |
| Day 20 ± 2 | Visit 5: Outcome lens #2, subjective and objective visual assessments and tear collection and tear collection | 75 minutes |

The anticipated duration to enroll and complete all study subjects is approximately 9-12 months. The estimated date for the investigators to complete analyses for this study is Fall/Winter 2021.

9.0 Study Endpoints

9.1 The primary study endpoints will compare toric to spherical lenses for:

- Near visual acuity

The secondary study endpoints will compare toric to spherical lenses for:

- Other near visual performance outcomes
 - Reading speed, reading sentences acuity, digital device interaction, dynamic visual acuity
- Subjective eye comfort and visual acceptance during contact lens wear
 - Association between subjective comfort surveys and tear TLB4 concentration

9.2 This is a minimal risk study so safety endpoints are not required

10.0 Procedures Involved

10.1 The study is a clinical trial and will be registered on ClinicalTrials.gov prior to subject enrollment.

10.2 Patients will be seen for 5 visits over a period of approximately 1 month. Visit 1 will determine subject eligibility for the study. Visits 2 and 4 are contact lens follow-up visits. Visits 3 and 5 are study outcome visits. Tests of visual performance at a near reading distance will be evaluated with an iPad application developed by [name]. These applications are designed for research purposes only and are not commercially available. The applications can measure reading speed and provide information on how a subject interacts with the electronic device (e.g. blink rate, working distance from the device, scrolling and zooming on the page, etc.).

10.3 Subjects will be randomized to start with either toric lenses or spherical correction (FDA approved lenses will be utilized).

Overview of Visit Procedures (Assessments)

FULL PROTOCOL TITLE: Toric Contact Lens Digital Performance and Comfort Study

A masked examiner will perform all outcome measures.

| | Visit 1 Baseline and Fit Lens 1 | Visit 2 day 3±1 | Visit 3 – day 10±2 | | Visit 4 day 13±1 | Visit 5 day 20±2 |
|--|--|-------------------------|-----------------------|---------------|-------------------------|---------------------|
| | | Follow- up Lens 1 | Outcomes Lens 1 | Fit Lens 2 | Follow- up Lens 2 | Outcomes Lens 2 |
| Informed consent | X | | | | | |
| Ocular/medical/contact lens history | X | | | | | |
| Ocular symptoms (CLDEQ-8) ⁸ | X | | X | | | X |
| Auto-refraction and keratometry | X | | | | | |
| Slit lamp exam with NaFl staining | X | | | | | |
| Manifest refraction | X | | | | | |
| Accommodation and phoria | X | | | | | |
| Near logMAR HCHL & LCHL acuity OU | X | | X | | | X |
| NAVQ survey ⁵ | X | | X | | | X |
| Radner reading sentences, dynamic acuity measurement and functional vision test with iPad ⁴ | X | | X | | | X |
| Tear collection | X | | X | | | X |
| Study lens order randomization | X | | | | | |
| Insertion of CL and settling (15 min) | X | | | X | | |
| Clinical CL vision and fit assessment, over-refraction, and power adjustment if indicated | X | X | | X | X | |
| Removal of study lens and slit lamp exam with NaFl staining | | X | X | | X | X |

FULL PROTOCOL TITLE: Toric Contact Lens Digital Performance and Comfort Study

| Layman's Description of Procedures | |
|---|--|
| Patient demographics | The subjects will be asked questions about their age, sex, race and ethnicity. |
| History | The subjects will be asked questions about their systemic and eye health and surgical history and medications. The subjects will be asked questions about how they use their current contact lenses, such as their current contact lens brand and wear time, as performed during a normal eye exam. |
| Questionnaires | Asks the subject about his/her vision and comfort during contact lens wear |
| Visual acuity | Measurements of how well subjects can detect letters or symbols at a given distance |
| Auto-refraction/keratometry | A machine will shine light into a subject's eye and will estimate their prescription and curvature of the eye without making contact with the eye. |
| Slit Lamp Exam | A specialized microscope is used to shine light on the eye and to examine the health of the front of the eye, including conjunctival and limbal redness using Cornea and Contact Len Research Unit (CCLRU) grading scale. Sodium fluorescein (NaFl) and lissamine green are temporary dyes that are used in routine contact lens exams to evaluate the health of the front surface of the eye using modified Oxford Scale. |
| Tear collection | Tears will be collected from both eyes using glass microcapillary tubes (BLAU_BRAND, Intramark, Wertheim, Germany) and pooled together in a low adhesion Eppendorf tube. The collected tears will be kept on ice and transferred to a -80°C freezer within half an hour and stored until batch analysis using Leukotriene B4 ELISA kits (dilution factor 1:10, Assay Designs, Ann Arbor, MI). ⁹ |
| Refraction | The subject's prescription is determined by placing different power lenses in front of the subject's eye, and modified according to the subject's responses. |
| Contact Lens Fitting | A contact lens is placed on the eye and the fit is assessed (how much it moves, where it sits on the eye, etc.). This is done using a slit lamp biomicroscope. |
| Contact Lens Over-Refraction and Power Adjustment | Lenses will be placed in front of the subject's eye while wearing the study contact lenses to determine if the prescription needs to be changed according to the subject's responses. The contact lens power will be adjusted if needed based on standard clinical fitting guidelines. |
| Radner Reading, functional vision tests, and dynamic acuity measurement | An iPad application will be used to assess reading performance (speed, accuracy, etc.). The dynamic acuity measurement (detection rather than a recognition task) involves a Landolt C surrounded by crowding bars presented for a limited duration |

FULL PROTOCOL TITLE: Toric Contact Lens Digital Performance and Comfort Study

| | |
|--|---|
| | (300ms) and the observer identifies which of the 4 possible directions it is orientated on a response keypad. An incorrect response leads to an increase in presentation size and correct response a decrease, with the endpoint being when there have been 3 reversals in the staircase procedure. |
|--|---|

11.0 Setting

11.1 All study visits will be conducted at the University of Houston College of Optometry in the [name] lab

12.0 Drugs or Devices

12.1 No investigational drugs or devices will be used in this study. The contact lenses used in the study are commercially available, FDA approved contact lenses that will be worn on a daily wear, daily disposable basis. An assistant will mask (over-label) contact lenses so that the subject and outcome examiner remain masked. The primary examiner will follow the manufacturer's fitting guide to determine the initial lens powers. Lens powers will be modified, as needed for best vision, according to the manufactures fitting guide.

The ophthalmic dyes used in the trial to evaluate the health of the front surface (sodium fluorescein and lissamine green) are a commercially available ocular diagnostic agents commonly used in routine clinical assessment of ocular health in optometry.

| Study Contact Lenses (Alcon) | Starting Sphere Power | Starting Cyl Power |
|-------------------------------------|--|---------------------------|
| Precision1 for Astigmatism | Vertexed manifest refraction | Per the fitting guide |
| Precision1 Sphere | Vertexed spherical-equivalent of manifest refraction | N/A |

